9.2.2 Secondary

Secondary endpoint questions include:

- The distribution of HCPs' reported levels of receipt and reading of the ENJAYMO™ Physician's Guide,
- HCPs' knowledge levels for each question regarding the information included in the ENJAYMO™ Physician's Guide (i.e., all questions relating to all domains), assessed as the percentages of HCPs with correct responses to each question,
- The distribution of HCP's reported levels of dissemination of the ENJAYMO™ Patient Guide to patients treated with ENJAYMO™ (questions asked to ENJAYMO™ prescribers only),
- The distribution of HCPs' responses regarding their experience with patients' receptivity to vaccination (questions asked to ENJAYMO™ prescribers only),
- Implementation of vaccination (questions asked to ENJAYMO prescribers only), and
- The distribution of responses regarding the primary source(s) from which HCPs learned about the information included in the ENJAYMO™ Physician's Guide.

Table 9-1 Outcomes/endpoints collected in the survey

Study Objective Domains Assessed	Corresponding variable	Operational definition/derivation "Calculated as the percentage of HCPs who"*
HCPs' knowledge of the indication for ENJAYMO™ treatment in adult patients with CAD (not patients with cold agglutinin syndrome)	Knowledge that ENJAYMO™ is indicated for the treatment of hemolytic anemia in CAD patients	For question 3: "Checked" hemolytic anemia
	Knowledge that ENJAYMO™ is not indicated for the treatment of jaundice	For question 3: "Not checked" jaundice
	Knowledge that ENJAYMO™ is not indicated for the treatment of cardiac arrhythmia	For question 3: "Not checked" cardiac arrhythmia
	Knowledge that ENJAYMO™ is not indicated for the treatment of nausea and vomiting	For question 3: "Not checked" nausea and vomiting
	Knowledge that ENJAYMO™ is not indicated for the treatment of patients with cold agglutinin syndrome	For question 3: "Not checked" indicated for patients with cold agglutinin syndrome

Study Objective Domains Assessed	Corresponding variable	Operational definition/derivation “Calculated as the percentage of HCPs who”*
HCPs’ knowledge of important potential risks of serious infections from encapsulated bacteria	Knowledge that ENJAYMO™ should only be prescribed to patients who have received appropriate vaccinations, especially against encapsulated bacteria	Checked “true” to question 4

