9.8 Data Management

Survey data collection will be completed on-line in Conformat, a software platform specifically designed for the creation and delivery of multi-lingual surveys. Data collected will be stored at secure servers and will be maintained to ensure compliance with applicable local and national regulations.

Response sets for multiple-choice questions will be randomised to minimise bias. To minimise likelihood that respondents would look up answers and/or discuss the survey while taking it, respondents will be asked to complete survey in 1 sitting and will not be allowed to revise their answers after they advance to the next question.

Survey database lock is anticipated to occur shortly after the survey is closed in all countries. To reduce opportunity for bias, survey respondents will not be contacted to clarify or revise their responses to knowledge assessment-related questions.

Data management will be in accordance with the ICON's standard operating procedures (SOPs). Additional details regarding data collection, management of missing data, data storage, and validation procedures will be detailed in the survey manual and statistical analysis plan (SAP).

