Please click on the NEXT button to verify that you qualify for this survey and to complete the required documentation for participation.

[BEGIN SURVEY SCREENING QUESTIONS]

S1. Does your practice include patients with cold agglutinin disease?

- Yes → **PROCEED TO S2**
- No → **PROVIDE A POP-UP THAT STATES** “Based on your answer, you are not eligible to take this survey. Please click “Next” to confirm your answer is correct, or click “Back” to review your answer”. **IF THE USER CLICKS ON ‘BACK’ THEN THE QUESTION WILL BE DISPLAYED AND THE RESPONSE CAN BE**

CHANGED. IF THE USER CLICKS ON ‘NEXT’ THEN THANK AND TERMINATE.

- S2. Do you provide your permission to share your anonymized survey responses, aggregated with all other survey responses, with the European Medicines Agency or national competent authorities?
- Yes → **PROCEED TO S3**
 - No → **PROVIDE A POP-UP THAT STATES** “Based on your answer, you are not eligible to take this survey. Please click “Next” to confirm your answer is correct, or click “Back” to review your answer”. **IF THE USER CLICKS ON ‘BACK’ THEN THE QUESTION WILL BE DISPLAYED AND THE RESPONSE CAN BE CHANGED. IF THE USER CLICKS ON ‘NEXT’ THEN THANK AND TERMINATE.**
- S3. Are you or have you been a direct employee of Sanofi, ICON, the European Medicines Agency, or other European-based National Competent Authorities within the past 5 years?
- Yes → **PROVIDE A POP-UP THAT STATES** “Based on your answer, you are not eligible to take this survey. Please click “Next” to confirm your answer is correct, or click “Back” to review your answer”. **IF THE USER CLICKS ON ‘BACK’ THEN THE QUESTION WILL BE DISPLAYED AND THE RESPONSE CAN BE CHANGED. IF THE USER CLICKS ON ‘NEXT’ THEN THANK AND TERMINATE.**
 - No → **PROCEED TO MAIN SURVEY**

[Termination Language for Non-Qualified Candidates:]

Thank you for your interest in participating in this survey. However, we are required to limit participation to healthcare professionals who meet the survey eligibility requirements. We look forward to your potential participation in a future survey.

[Language for Qualified Candidates:]

Thank you for your responses. You qualify for this survey, and we look forward to your participation. Once you enter the main survey, you will only be able to move forward through the questions.

[END SURVEY SCREENING QUESTIONS]

MAIN SURVEY

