[Preamble 1]: These questions are about the risks of serious infections and meningococcal infections associated with ENJAYMO™ (sutimlimab). Please be sure to review all response choices for each question before answering each question. Please note that you will only be able to move forward in the survey as you complete each question.

CORRECT RESPONSES ARE CHECKED ✓

1. Did you receive the “ENJAYMO™ Physician’s Guide” that provides information to minimise the risks of serious infections and meningococcal infections associated with product use?
 - Yes
 - No
 - I don’t know/am not sure

2. Did you read the “ENJAYMO™ Physician’s Guide” that provides information to minimise the risks of serious infections and meningococcal infections associated with product use?
 - Yes
 - No
 - I don’t know/am not sure

3. ENJAYMO™ (sutimlimab) is indicated in adult patients with cold agglutinin disease (CAD) for the treatment of (Check all that apply) **RANDOMIZE ORDER OF THE FIRST 5 RESPONSES**
 - Hemolytic anaemia
 - Jaundice
 - Cardiac arrhythmia
 - Nausea and vomiting
 - Cold agglutinin syndrome
 - I don’t know/am not sure

4. ENJAYMO™ (sutimlimab) should only be prescribed to patients who have received appropriate vaccinations, especially against encapsulated bacteria.
 - True
 - False
 - I don’t know/am not sure

5. Are you familiar with current local guidelines or recommendations in patients with persistent complement deficiencies for meningococcal conjugate vaccine(s), meningococcal serogroup B vaccine(s), and pneumococcal vaccine(s)?

Yes
 No
 I don't know/am not sure

6. According to the ENJAYMO™ (sutimlimab) **Summary of Product Characteristics** and the “**ENJAYMO™ Physician’s Guide**”, which of the following warrant specific caution when using ENJAYMO™ (sutimlimab)? Please select all that apply.

Neisseria meningitides infection
 Hemophilus influenza infection
 Streptococcus pneumoniae infection
 Urinary tract infection
 All of the above
 I don't know/am not sure

7. According to the “**ENJAYMO™ Physician’s Guide**”, which of the following are important activities that are necessary when using ENJAYMO™ (sutimlimab):

		Yes, needs to be monitored	No, does not need to be monitored	I don't know/am not sure
A	Monitor patients for kidney damage			

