[ON-LINE SURVEY - PROGRAMMER: RANDOMISE THE ORDER OF THE FIRST 5 RESPONSE OPTIONS]

HCP CHARACTERISTICS

[Preamble 2]: Below are 7 additional questions to help us combine your answers with other answers we have received, and to help us interpret the survey results. **THERE ARE NO CORRECT RESPONSES TO QUESTIONS 10, 11, 19, and 20. DISPLAY QUESTIONS 12-18 ON THE SAME PAGE.**

10. Approximately how many years have you been practicing as a physician?
- <5 years
 - 5 to <10 years
 - 10 to <15 years
 - ≥15 years
 - Prefer not to answer
11. Approximately how many patients have you treated with ENJAYMO™ (sutimlimab)?
- None → **PROCEED TO QUESTION 20**
 - < 5 patients → **PROCEED TO QUESTION 12**
 - 5-10 patients → **PROCEED TO QUESTION 12**
 - >10 patients → **PROCEED TO QUESTION 12**
 - Prefer not to answer → **PROCEED TO QUESTION 20**
12. For the most recent patient you prescribed ENJAYMO™ (sutimlimab), did you provide the patient with a copy of the ENJAYMO™ Patient Guide?
- Yes → **PROCEED TO QUESTION 13**
 - No → **PROCEED TO QUESTION 13**
 - I don't know/am not sure → **PROCEED TO QUESTION 13**
13. For the most recent patient you prescribed ENJAYMO™ (sutimlimab), did you confirm that their vaccination status is up-to-date according to local guidelines or recommendations for patients with persistent complement deficiencies?
- Yes → **PROCEED TO QUESTION 14**
 - No → **PROCEED TO QUESTION 19**
 - I don't know/am not sure → **PROCEED TO QUESTION 19**

14. For the most recent patient you prescribed ENJAYMO™ (sutimlimab), which vaccines did you check the status of? Please select all that apply.
- Meningococcal conjugate vaccine(s)
 - Meningococcal serogroup B vaccine(s)
 - Pneumococcal vaccine(s)
 - Other (not listed above); specify: _____
 - I don't know/am not sure
15. For the most recent patient you prescribed ENJAYMO™ (sutimlimab), was the patient up-to-date on their vaccinations?
- Yes → **PROCEED TO QUESTION 19**
 - No → **PROCEED TO QUESTION 16**
 - I don't know/am not sure → **PROCEED TO QUESTION 19**
16. For the most recent patient you prescribed ENJAYMO™ (sutimlimab), did you administer or prescribe vaccines to the patient?
- Yes → **PROCEED TO QUESTION 18**
 - No → **PROCEED TO QUESTION 17**
 - I don't know/am not sure → **PROCEED TO QUESTION 19**
17. For the most recent patient you prescribed ENJAYMO™ (sutimlimab), what was the reason you did not provide vaccination?
- The patient refused vaccination → **PROCEED TO QUESTION 19**

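### Annex 3 puts questions 12 to 18 on one page, which conflicts with the protocol's own forward-only, no-revision rule for the survey (minor; prescriber-only secondary endpoints)

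*Protocol*

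**What the plan says.** Three statements in the protocol set a forward-only rule:

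- Section 9.8 (Data Management): respondents "will not be allowed to revise their answers after they advance to the next question". The stated aim is "To minimise likelihood that respondents would look up answers and/or discuss the survey while taking it".
- Annex 3, message to qualified respondents after screening: "Once you enter the main survey, you will only be able to move forward through the questions".
- Annex 3, Preamble 1: "Please note that you will only be able to move forward in the survey as you complete each question".

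A fourth statement, the programming note under the HCP characteristics heading in Annex 3, says "DISPLAY QUESTIONS 12-18 ON THE SAME PAGE".

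These seven questions ask about the patient most recently prescribed the product: Patient Guide given (12), vaccination status confirmed (13), vaccines checked (14), vaccinations up to date (15), vaccines administered or prescribed (16), reason if not (17) and timing (18). Most carry skip instructions; at question 13, for example, "No → PROCEED TO QUESTION 19".

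Section 9.2.2 lists the secondary endpoints that they feed, among them "Implementation of vaccination (questions asked to ENJAYMO prescribers only"), Patient Guide dissemination and patients' receptivity to vaccination.

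**The concern.** The forward-only rule is written for questions and for the whole main survey. Questions 12 to 18 are part of that survey and no exception is stated. Putting all seven on one page takes away the step from one question to the next at which an answer would become final.

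These items are self-reports of what the prescriber did, and section 9.11 names social desirability as a limitation of self-report. A prescriber who can look at the follow-up items on vaccines checked, action taken and timing, and then return to question 13, has an opportunity to adjust that the rule would otherwise have closed. The endpoints rest on very few respondents, so a single altered answer shows in the reported percentage.

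**Working it through.** **1. The texts side by side**

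- Section 9.8: an answer is final once the respondent moves to the next *question*.
- Message on entering the main survey: forward movement only, through the *questions*.
- Preamble 1: forward movement as each *question* is completed.
- Annex 3 note: seven questions share one *page*.

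The first three use the question as the unit. The fourth allows free movement among seven questions unless something else prevents it, and no per-answer lock is specified.

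**2. The printed routing inside the block**

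- Question 13, No or not sure: go to 19 (skips 14 to 18).
- Question 15, Yes or not sure: go to 19 (skips 16 to 18).
- Question 16, Yes: go to 18 (skips 17); No: go to 17; not sure: go to 19.
- Question 17, refused or not sure: go to 19 (skips 18); vaccinated elsewhere: go to 18.

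**3. What each way of building the page would do**

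- *Static page, no lock:* earlier answers can be revised, and items off the respondent's route are visible and answerable. Neither the no-revision rule nor the routing is respected.
- *Conditional page, no lock:* routing is respected on the first pass. The respondent can still answer 13, see what opens, and return to 13. The no-revision rule is not respected.
- *Conditional page, each answer locked:* both are respected.
- *One question per screen, forward only:* both are respected.

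The protocol does not say which is intended. The no-revision conflict is present in both unlocked builds; the routing conflict is present only in the static one.

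**4. Scale**

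The protocol's own precision figure comes first, although the point does not depend on it. The simple asymptotic half-width is 1.96 × √(p(1 − p)/n). With p = 0.80 and n = 50 this is 1.96 × √(0.16/50) = 0.111, or 11.1 points, as section 9.7 states.

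Questions 12 to 18 go to prescribers only, and section 9.7 puts their number at possibly 10:

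- Half-width at p = 0.80, n = 10: 1.96 × √(0.16/10) = 0.248, or 24.8 points. The exact 95% interval for 8 of 10 is 44.4% to 97.5%.
- One changed answer to question 12 or 13: 1/10 = 10 percentage points.
- For questions 14 to 18, routing leaves m ≤ 10 respondents, so one answer weighs 100/m points, that is, at least 10. The protocol gives no value for m.

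These figures show how much one answer weighs. They do not predict how many answers would change.

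**5. What is not touched**

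The primary composite uses questions 3 to 8 (section 9.2.1). Question 19, on counselling, lies outside the shared page.

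**The case against.** The best defence is that the no-revision rule serves a narrower purpose. Section 9.8 aims it at looking up or discussing answers, which matters most for the knowledge items. Questions 12 to 18 report behaviour and come under their own preamble, so Preamble 1 is weak support. This lowers the importance of the point. It does not remove the conflict, because neither the wording in section 9.8 nor the message on entering the main survey is limited to knowledge items.

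The rule could also be read as applying to pages, so that answers become final on leaving a page. The texts speak of questions, and on that reading the rule would do nothing within this block.

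The added cue is modest as well. Questions 4 and 5 have already shown the vaccination message and the same three vaccine classes that question 14 lists, and questions 12 and 13 reveal the favourable answer in their own wording. What the shared page adds is mainly the follow-up structure and the timing options in question 18. Showing one question per screen would not remove social desirability bias, which section 9.11 already discloses. All of this stands.

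Three stronger readings may tempt a reader, and the document does not support them:

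- *The note contradicts the routing, and every prescriber sees the whole checklist before answering.* This holds only for a static page. Routing can run on one page with conditional display, and the protocol does not say that the page is static.
- *The denominators for questions 14 to 18 are contaminated by off-route answers.* This rests mainly on the same assumption. Section 9.8 also leaves details of data collection and validation to the survey manual and the SAP, so the absence of a rule on off-route answers is not a defect of this protocol.
- *A few changed answers could carry an item over 80%.* Sections 9.2.1 and 9.9.1.2 apply the 80% criterion to the primary endpoint. The items here are analysed descriptively and have no success threshold.

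**Conclusion.** The conflict between the one-page note and the forward-only, no-revision rule is real and follows from the text alone. Its practical consequence, that question 12 or 13 can be changed after the follow-up items have been seen, assumes an ordinary page without per-answer locking. Exposure to items that should be skipped needs the further assumption that the page is static.

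The reach is limited to the descriptive secondary endpoints on Patient Guide dissemination and on receptivity to and implementation of vaccination. With possibly 10 prescribers, each changed answer to question 12 or 13 is worth about 10 percentage points. How many would change is unknown, and the protocol offers no basis for an estimate. The primary endpoint is unaffected. Severity: minor.

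**What to change.** Replace the programming note so that questions 12 to 18 are shown one at a time, forward only, with the printed routing enforced. An equally consistent alternative keeps one page but reveals each item only when the routing reaches it and locks each answer once given. Either version brings the block into line with section 9.8 and with the message shown on entering the main survey.

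If the sponsor prefers an ordinary shared page, section 9.8 and the respondent-facing text should state the exception. That would reconcile the documents but leave the opportunity to revise in place.

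The change is a programming instruction. Its cost is a few more screens for the small number of prescribers who reach these questions.

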To endeavor to achieve a sample of at least 50 completed surveys, recruitment will remain open for a minimum of 3 months and up to 6 months in each country, and will not be closed early even if 50 completed surveys have been reached sooner. Metrics will be tracked to monitor survey progress (e.g., number of eligible/ineligible HCPs, number of completed surveys). Depending on response rates, follow-up reminders will be sent to non-respondents to achieve the target sample size. If after two reminders the target sample size has not been reached, the pool of potential HCP prescribers will be supplemented through additional outreach based on internet research or outreach through applicable professional societies, inclusion of additional countries within the European Union (EU)/European Economic Area (EEA), or extension of the survey period. The local teams of medical scientific liaison from Sanofi may also support the survey by reaching out to some of the HCPs contacted and whom they may already know or visit, so to encourage their participation.

The survey may be conducted in up to 2 waves. In the event that the survey has been open for 6 months in all countries and 30 completed surveys have not been achieved, with a minimum

of 10 of those having been completed by ENJAYMO™ prescribers, a second wave of the same survey will be conducted 6 to 12 months later.

Invitations to participate in the survey may be sent to up to 1,000 HCPs by either email (preferred) or by post mail (if email is not available) using the available contact information. The invitation letter will include information about the survey, a unique code, and instructions for accessing the survey. The unique code will be used to track who has already completed a survey so that reminders are only sent to HCPs who have not yet completed the survey.

As an acknowledgement of their time and valuable input, HCPs who complete the survey will receive fair market value (FMV) compensation if allowed, feasible, and in accordance with local regulations.

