9.2.3 Other Endpoints

The survey includes HCP characteristics and other outcomes that may be treated as covariates for data analysis. These questions are described in Table 9-2.

Table 9-2 Other outcomes collected in the survey

Data collected	Variable type	Operation definition/derivation
Years practicing as a physician	Categorical	< 5 years, 5 to <10 years, 10 to <15 years, ≥15 years, prefer not to answer
Number of patients for which the HCP has prescribed ENJAYMO™	Categorical	None, <5 patients, 5-10 patients, >10 patients, prefer not to answer
HCP confirmed distribution of the ENJAYMO™ Patient Guide	Categorical	Yes, no, I don’t know/am not sure
HCP confirmed vaccination status in the patient most recently prescribed ENJAYMO™	Categorical	Yes, no, I don’t know/am not sure
Vaccines HCP checked in the patient most recently prescribed ENJAYMO™	Categorical	Meningococcal conjugate vaccine(s), meningococcal serogroup B vaccine(s), pneumococcal vaccine(s), Other (please specify), I don’t know/am not sure
Vaccines up-to-date in the patient most recently prescribed ENJAYMO™	Categorical	Yes, no, I don’t know/am not sure
HCP administered or prescribed vaccines to the patient most recently prescribed ENJAYMO™	Categorical	Yes, no, I don’t know/am not sure
Reason HCP did not provide vaccines to the patient most recently prescribed ENJAYMO™	Categorical	The patient refused vaccination, the patient received vaccination elsewhere, I don’t know/am not sure
Timing of vaccination relative to starting ENJAYMO™ in the patient most recently prescribed ENJAYMO™	Categorical	At the same time ENJAYMO™ treatment was started, less than two weeks before ENJAYMO™ treatment was started, two weeks before ENJAYMO™ treatment was started, I don’t know/am not sure

HCP counselled the patient most recently prescribed ENJAYMO™ to seek immediate medical attention if they experience symptoms of serious infection	Categorical	Yes, no, I don't know/am not sure
Investigator in ENJAYMO™ clinical trial	Categorical	Yes, no, prefer not to answer
Involvement with CADENCE patient registry	Categorical	Yes, no, prefer not to answer

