9.4 Study Population

Generally, it is preferable to conduct surveys to assess HCPs' knowledge and awareness of product-specific aRMM amongst HCPs actually engaging with the product (e.g., prescribers or HCPs managing care for patients receiving the product). However, since ENJAYMO™ is used to treat CAD, a rare disease, and will also be a newly authorised product where reimbursement applications and decisions will be ongoing, the number of prescribers may be low and therefore it may be challenging to identify a sufficient number of HCP prescribers to obtain robust and precise estimates of knowledge level. This survey will therefore be open to any HCP who was targeted to receive the aRMM for the product and is likely to prescribe (even though may not have yet prescribed) ENJAYMO™.

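### Question 11 asks about patients treated, but the variable it supplies is patients prescribed, so an HCP who treated without prescribing could be counted as a prescriber

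*Protocol*

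**What the plan says.** Annex 3, Question 11 asks: "Approximately how many patients have you treated with" ENJAYMO. The answers are none, fewer than 5, 5 to 10, more than 10, and prefer not to answer. Section 9.2.3, Table 9-2 lists a variable with those same categories but names it "Number of patients for which the HCP has prescribed ENJAYMO™".

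The routing depends on Question 11. Each non-zero answer goes on to the next item, for example "< 5 patients → PROCEED TO QUESTION 12". None and prefer not to answer both skip to Question 20. Questions 12 to 19 are all framed by prescribing; Question 12 begins "For the most recent patient you prescribed ENJAYMO™ (sutimlimab), did you provide the patient with a copy".

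The objectives and endpoints (Sections 8.2 and 9.2.2) restrict Patient Guide dissemination, patients' receptivity to vaccination and vaccination implementation to prescribers. Section 8.2 adds counselling. Sections 9.9.1.2 and 9.11 stratify by prescribing status. Section 9.1.1 and the Synopsis (Data Sources) attach to the second-wave rule a minimum "of 10 of those having been completed by ENJAYMO" prescribers. Section 9.7 expects possibly 10 prescribers among 50 completed surveys.

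**The concern.** The question and the variable it feeds measure different things. Treating a patient with a drug and prescribing it usually coincide, but not always: one physician may start the drug and another may manage the patient on it. A respondent in the second position can truthfully give a non-zero answer to Question 11 and would then be recorded under a heading that says prescribed.

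That respondent would next be asked about a patient they had prescribed for, with no suitable answer available. A reply of No or not sure would stand in for not applicable. Nothing in the data would separate it from a prescriber's genuine No.

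At stake are the prescriber-only descriptive endpoints, the comparison of knowledge by prescribing status, and the prescriber count in the second-wave rule where that count applies. The stratum is expected to be small, so a single respondent carries visible weight.

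**Working it through.** **1. Does any other item supply prescriber status?**
- Screening question S1 asks only whether the practice includes patients with cold agglutinin disease. S2 and S3 concern permission and employment.
- Section 9.4.2 admits potential prescribers, so eligibility does not settle the status.
- Questions 12 to 19 presuppose a prescription but do not ask whether there was one. None offers an answer meaning 'have not prescribed'.
- Questions 20 and 21 ask about trial and registry involvement.

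Question 11 is therefore the only source. The protocol does not say outright that it defines prescriber status. That follows from Table 9-2, the routing and the absence of any alternative.

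**2. Can the respondent or the analyst correct it later?** Annex 3 is forward-only, and Section 9.8 bars revising an answer after advancing. A respondent who first meets the word 'prescribed' at Question 12 cannot return to Question 11. An analysis plan cannot recover a status that the survey did not collect.

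**3. The plan's own precision figure.** Section 9.7 gives 11.1% for 50 HCPs at 80%, using the simple asymptotic formula:
- half-width = 1.96 × √(p(1 − p)/n)
- n = 50, p = 0.80: 1.96 × √(0.16/50) = 0.111, or 11.1 points. This reproduces the stated figure.

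The same formula for a stratum of 10 gives 1.96 × √(0.16/10) = 0.248, or 24.8 points.

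**4. Illustration of the effect (assumed values).** Suppose 10 respondents are counted as prescribers, m of them treated without prescribing, the true result among prescribers is 80%, and a proportion q of the m answer positively. Only the stratum size of about 10 comes from the protocol; m, q and the 80% are assumptions.

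Expected observed result = [(10 − m) × 0.80 + m × q] / 10

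| m | q = 0 | q = 1 | True prescribers left | Half-width at 80% |
|---|---|---|---|---|
| 0 | 80% | 80% | 10 | 24.8 points |
| 1 | 7.2/10 = 72% | 8.2/10 = 82% | 9 | 26.1 points |
| 2 | 6.4/10 = 64% | 8.4/10 = 84% | 8 | 27.7 points |
| 3 | 5.6/10 = 56% | 8.6/10 = 86% | 7 | 29.6 points |

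The error can move the result in either direction.

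**5. The second-wave count.** With 8 true prescribers and 2 treating non-prescribers, 8 + 2 = 10 would be counted and the minimum would appear to be met. This matters only under the rule in Section 9.1.1 and the Synopsis (Data Sources). Section 9.3 and the Synopsis (Study Design) trigger the second wave on fewer than 30 completed surveys, with no prescriber condition.

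**6. The reverse error.** An HCP who has prescribed but whose patient has not yet started treatment could answer none, and would be routed past Questions 12 to 19.

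**The case against.** The strongest reply is that the feared reading is unlikely. The survey introduction in Annex 3 describes the survey as being among HCPs who prescribe the product. Question 10 addresses the respondent as a physician, and a physician asked how many patients they have treated with a drug will often count those they put on it. The protocol otherwise divides its respondents into prescribers and those who have not yet prescribed. This makes the problem less likely, but it does not make the two wordings equivalent.

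A reader might take Section 9.4, which mentions "prescribers or HCPs managing care for patients receiving the product", as proof that treating non-prescribers are expected in this sample. It is not. The phrase is an example inside a general remark about surveys of this kind, and the same section goes on to describe this survey's respondents as those likely to prescribe. It shows only that the protocol recognises the two roles.

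A reader might also infer a systematic fall in the prescriber results. If 9 of 10 prescribers answered positively (90%), adding one, two or three respondents who all answer No or not sure gives 9/11 = 82%, 9/12 = 75% and 9/13 = 69%. The arithmetic is right but one-sided. An HCP managing a patient on treatment may well have checked vaccination or given counselling, so the effect can go either way.

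The prescriber-only endpoints are secondary and descriptive with no success threshold, and Section 9.11 already warns of few responses and low precision for them. Against a half-width of about 25 points, one misclassified respondent is a modest addition. All of this stands, and it limits the weight of the point.

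**Conclusion.** The inconsistency between Question 11 and Table 9-2 is real. Because no other item records prescribing, it leaves open a misclassification that later analysis cannot undo. The documents support saying that a treating non-prescriber *could* be counted as a prescriber. They do not support saying that such respondents are present: no number or rate is given, and it may be zero.

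The consequences are confined to the prescriber-only secondary endpoints, the stratification by prescribing status, and the second-wave prescriber count in the two places that state it. A reader might fear for the main result, but the overall primary composite rests on Questions 3 to 8 (Section 9.2.1), which every respondent meets before Question 11. Only its breakdown by prescribing status is exposed.

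On size, one misclassified respondent among 10 counted, with an assumed true result of 80%, shifts the expected value by between −8 and +2 points (72% to 82%). This is a minor point, worth correcting because the correction is so cheap.

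**What to change.** Reword Question 11 to match the definition in Table 9-2, for example: *For approximately how many patients have you prescribed ENJAYMO (sutimlimab)?* The answer categories and the routing can stay as they are. The question, the analysis variable, the lead-in to Questions 12 to 19 and the prescriber count would then share one definition.

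The cost is one reworded sentence in the questionnaire, its re-translation, and the proof-reading and local affiliate sign-off that Section 9.1.2 requires in each country. It adds nothing to respondent burden or sample size. It is best done before the survey opens, because answers already given to the present wording cannot be reclassified.
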